9.1.4.3. Use of Study Provided Blood Glucose Meter

The Study SMBG meter must be used to

- Collect 10-point SMBG profiles (Table ITRO.5)
- Confirm hypoglycemia events (glucose value ≤ 70 mg/dL)
- Confirm all hyperglycemia events (glucose value > 300 mg/dL)
- Calibrate the Dexcom CGM every 12 hours during blinded CGM sessions
- Test SMBG at the time of each unplanned infusion set change for any reason

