ULN	upper limit of normal
Unexplained Hyperglycemia	High blood glucose (≥ 300 mg/dL) that cannot be explained by a missed prior bolus, dietary indiscretion, rebound or treatment of hypoglycemia, a pump failure, an empty pump reservoir, an infusion set complication (e.g.; kinked, came out, leaking), or an infusion site complication (e.g.; pain, redness).
VAS	visual analog scale

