11. To compare LY900014 and Humalog with respect to 10-point SMBG profiles	11. Change from baseline 10-point SMBG values at Week 16
12. To compare LY900014 and Humalog with respect to total, basal, and bolus insulin dose	12. Change from baseline in bolus/total insulin dose ratio at Week 16
13. To compare LY900014 and Humalog with respect to the proportion of patients achieving HbA1c targets	13. The proportion of patients with HbA1c <7% and ≤6.5% at Week 16
14. To compare LY900014 and Humalog with respect to the duration of time spent in hypoglycemic glucose ranges, obtained from CGM use	14. Duration (in minutes) and percentage of time with glucose values <54 and <70 mg/dL (3.0 and 3.9 mmol/L), normalized to a 24-hour period and number of episodes, defined as at least 10 consecutive minutes <54 and <70 mg/dL, from each 14-day CGM session at Week 16
15. To compare LY900014 and Humalog with respect to the duration of time spent in hyperglycemic glucose ranges, obtained from CGM use	15. Duration (in minutes) and percentage of time with glucose values >180 and >250 mg/dL (10.0 and 13.9 mmol/L), normalized to a 24-hour period and number of episodes, defined as at least 10 consecutive minutes >180 and >250 mg/dL, from each 14-day CGM session at Week 16
16. To compare LY900014 and Humalog with respect to the incidence and rate of pump occlusion alarms that lead to an unplanned infusion set change	16. Rate (events/patient/30 days) and incidence (percent of patients with at least 1 event) of pump occlusion alarms that lead to an unplanned infusion set change from baseline through Week 16
17. To compare LY900014 and Humalog with respect to the incidence and rate of episodes of unexplained hyperglycemia that lead to an unplanned infusion set change	17. Rate (events/patient/30 days) and incidence (percent of patients with at least 1 event of unexplained hyperglycemia > 300 mg/dL confirmed by SMBG that leads to an unplanned infusion set change from baseline through Week 16
Tertiary/Exploratory	
18. To compare the safety of LY900014 and Humalog	18. Adverse events, vital signs, chemistry, and hematology laboratory measures
19. To compare the incidence of treatment-emergent positive anti-insulin lispro antibodies for LY900014 and Humalog	19. Incidence of treatment emergent anti-insulin lispro antibodies

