6.12.6.2. Infusion Set Changes

To handle potential missing input in paper diary for the infusion set changes, time intervals until infusion set change that are greater than 7 days (168 hours) will be excluded from the analysis. If 2 planned infusion set changes happened on the same day at the same time, only 1 will be used for analysis. The same rule applies when there are duplicate unplanned infusion set changes.

The incidence (percent of patients with at least 1 event) and rate for overall, planned and unplanned infusion set changes will be analyzed using Fisher's exact test and Wilcoxon signed-rank test respectively. The unplanned infusion set changes will be analyzed for any reason and for each individual reason (pump occlusion alarm, unexplained high BG, infusion site reaction (pain, redness or swelling at infusion site), infusion set problem (infusion set kinked, pulled out, leaking, reservoir empty, etc.). The unplanned infusion set changes will also be summarized by infusion set wear day (Day1 = \leq 24 hours, Day2 = $>$ 24 and \leq 48 hours, Day3 = $>$ 48 and \leq 72 hours and Day3+ = $>$ 72 hours) by treatment and treatment comparison will only be conducted when there are sufficient number of patients in each treatment arm. A listing of all unplanned infusion set changes will be generated for the enrolled population. For each unplanned infusion set change, the following information will be provided:

- Cannula length at study entry
- Cannula length at the time of the infusion set change
- BG at time of infusion set change
- the reason for the infusion set change
- the infusion set wear day on which the infusion set change occurs
- the ketone test value associated with the infusion set change when SMBG $>$ 300 mg/dL

A table will be generated to summarize number of patients who have at least 1 unplanned infusion set change due to unexplained high BG with BG (SMBG) $>$ 250 mg/dL (13.9 mmol/L) and with BG (SMBG) $>$ 300 mg/dL (16.7 mmol/L).

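### The SAP specifies no rate analysis for secondary endpoint 17 as defined: the >300 mg/dL, SMBG-confirmed condition is used only for a count of patients

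*SAP*

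**What the plan says.** **The endpoint.** The protocol (Synopsis and Table ITRO.2) and the SAP (Table ITRO 4.1) word endpoint 17 alike: "Rate (events/patient/30 days) and incidence (percent of patients with at least 1 event of unexplained hyperglycemia > 300 mg/dL confirmed by SMBG", where the episode leads to an unplanned set change between baseline and Week 16.

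**The planned comparison.** SAP 6.12.6.2 names the tests. Incidence and "rate for overall, planned and unplanned infusion set changes will be analyzed using Fisher's exact test and Wilcoxon signed-rank test respectively". It then extends the analysis to reasons: "The unplanned infusion set changes will be analyzed for any reason and for each individual reason (pump occlusion alarm, unexplained high BG", followed by infusion site reaction and infusion set problem. It attaches no glucose value to the high-glucose reason.

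**Where 300 mg/dL appears in that section.** It appears twice. One place is a patient-level table: "A table will be generated to summarize number of patients who have at least 1 unplanned infusion set change due to unexplained high BG", with SMBG >250 mg/dL and with SMBG >300 mg/dL. The other is the listing of unplanned changes, which shows "the ketone test value associated with the infusion set change when SMBG" is >300 mg/dL.

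**The protocol definition.** Appendix 1 describes unexplained hyperglycemia as blood glucose >=300 mg/dL "that cannot be explained by a missed prior bolus, dietary indiscretion, rebound or treatment of hypoglycemia", or by several pump and infusion-set causes.

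**The concern.** Objectives 16 and 17 are the two secondary objectives about failed pump delivery. Protocol 3.3 explains their importance: ketoacidosis can develop quickly when pump delivery is interrupted, and a high glucose that does not respond to a correction bolus may signal an occlusion or pump problem.

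Endpoint 17 has four elements: the episode is unexplained, above 300 mg/dL, SMBG-confirmed, and followed by an unplanned set change. The SAP's rate comparison explicitly carries only the first and last. The rate reported against objective 17 could therefore describe a broader event than the one named. The choice among >300, >=300 and no threshold would be left to whoever programs the table. For a pump-safety objective, the reader should know which event the between-group result refers to.

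**Working it through.** No sample size, power or expected rate is stated for objective 17, so there is no figure to reproduce. The check compares the definition with each place where set changes are analysed.

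**1. Elements of the endpoint against the analyses in SAP 6.12.6.2**

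| Element of endpoint 17 | By-reason comparison | Patient-count table |
|---|---|---|
| Unexplained high glucose as the reason | Yes | Yes |
| >300 mg/dL | Not stated | Yes, in one of two rows |
| SMBG value | Not stated | Yes |
| Incidence | Yes | Yes, as a number of patients |
| Rate | Yes, no time unit stated | No |
| Between-group test | Fisher for incidence, Wilcoxon signed-rank for rate | None named here; the default in SAP 6.12 can apply |

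Neither column combines a rate with the >300 condition. The count cannot supply one, because a patient with a single qualifying change and a patient with several each count once.

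**2. Does another section fill the gap?** Protocol 10.3.4 specifies a negative binomial model per 30 days and a logistic model, but for occlusion alarms only. SAP 6.12.6.1 concerns time between changes. SAP 6.14.3 covers subgroups for unplanned changes, with no glucose threshold. None gives a rate for the objective 17 event.

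**3. Does Protocol Appendix 1 supply the threshold?** The SAP's four reasons match the four diary reasons in Protocol 9.1.4.4, so unexplained high BG corresponds to the protocol's unexplained hyperglycemia. If Appendix 1 governs, every event in the category is already >=300 mg/dL. The category then differs from the endpoint only at a reading of exactly 300, and where no SMBG was recorded.

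The SAP's own table tests that reading. If all events were >=300, any patient with a recorded reading would fall in the >250 row. The >300 row would lose only patients whose readings were all exactly 300, so the two rows would be almost identical. Planning both suggests that the authors expected readings below 300 under this reason. That is evidence, not proof. SAP 6.12.6.2 neither cites the definition nor uses its term.

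**4. Can the defined event be derived?** Yes. Protocol 9.1.4.3 requires the study meter for this purpose: "Test SMBG at the time of each unplanned infusion set change for any reason". Protocol 9.1.4.4 sends the result to the diary, and SAP 6.12.6.1 confirms that glucose and reason reach the eCRF.

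**The case against.** The strongest reply is that the protocol already fixes the threshold. The reason lists match one to one, Appendix 1 sets >=300 mg/dL, and SMBG is required at every unplanned change. On that reading, a change made at a moderate glucose does not belong in the category, and the by-reason rate is close to the endpoint. This is a fair reading and may describe practice. It does not settle the matter, because the SAP does not adopt the definition and its >250 row points the other way.

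A second reply concerns incidence, and it stands. SAP 6.12 provides Fisher's exact or Pearson's chi-square tests for categorical safety variables unless otherwise specified. The >300 patient count is such a variable, with the right threshold and an SMBG value. The gap is therefore in the rate.

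A third reply is that objective 17 is an other secondary objective with no multiplicity adjustment (SAP 6.5). That also stands and limits the consequence.

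A reader might infer more than the documents support:

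- *The comparison counts changes at any glucose value.* The SAP states no threshold, which is not the same as saying that none applies.
- *The endpoint is never analysed.* The by-reason rate contains the endpoint's events, and the patient count can be tested.
- *The treatment difference is diluted by a calculable amount.* That requires the share of changes made at or below 300 mg/dL and the rate ratio among them. The documents give neither, and under Appendix 1 the share could be near zero.
- *Changes at moderate glucose reflect habit rather than failed delivery.* Nothing in the documents supports this.

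**Conclusion.** The point holds in a limited form. SAP 6.12.6.2 specifies a rate comparison for a recorded reason, and a patient count for the reason plus the threshold, but no rate for the event that defines endpoint 17. The per-30-day unit is also missing there.

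The numerical effect cannot be stated. If Appendix 1 was applied when reasons were recorded, it is close to nil. If not, it depends on how many changes for this reason were made at or below 300 mg/dL or without a reading. No dilution figure should be quoted. The conclusion rests on the text of the two documents and on no assumed event rate. It affects one secondary safety objective, not the primary or multiplicity-adjusted results, and is worth correcting because the remedy is cheap.

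**What to change.** In SAP 6.12.6.2:

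1. Define the objective 17 event as an unplanned set change with reason unexplained high BG and a recorded SMBG >300 mg/dL, from baseline through Week 16.
2. Run the between-group comparisons of rate (events per patient per 30 days) and incidence on that event, naming the method for each. The signed-rank test now named for rates is a paired test, so the choice of method for two parallel groups needs its own correction.
3. Keep the unrestricted by-reason analysis as supportive.
4. Reconcile >300 in the endpoint with >=300 in Protocol Appendix 1, so that one cut-off applies throughout.

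The cost is SAP wording and one filter on data already collected. The restricted event will be no more frequent than the unrestricted one, so fewer events and a wider interval should be expected. Changes with no recorded SMBG would fall outside the event, so their number should be reported by group.

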6.12.6.3. Infusion Set Model and Cannula Length

A listing of infusion set model and cannula length changes will be generated. For each cannula length change, the following information will be included but not limited to:

- Date and time of the change
- Infusion set model before and after the change
- Cannula length before and after the change
- Exposure days to IP before and after the change
- Number of infusion site reactions (with severity) before and after the change

- Number of unplanned infusion set changes due to “Infusion Site Reaction (Pain, Redness or Swelling at Infusion Site)” or due to “Infusion Set Problem (Infusion Set Kinked, Pulled Out, Leaking, Reservoir Empty)” before and after the change

A summary table of infusion model/cannula length, number of infusion site reaction, and number of unplanned infusion set changes will be generated by treatment before and after infusion set model and/or cannula length change.

6.12.7. Immunogenicity

Blood samples for immunogenicity testing will be collected to determine antibody production against insulin lispro for all enrolled patients since Visit 4 prior to the first dose of study-provided prandial insulin treatment. Therefore, the blood sample result at Visit 4 will be considered as the anti-insulin lispro level at baseline for this study. The assessment of immunogenicity will include analyses of treatment-emergent anti-insulin lispro antibody up to Visit 801.

6.12.7.1. Treatment Emergent Anti-Insulin Lispro Antibody

The treatment-emergent anti-insulin lispro antibody (denoted as treatment-emergent antidrug antibody [TEADA] throughout this SAP) is based on the change from baseline (Visit 4) to post-baseline (post-Visit 4) in the anti-insulin lispro antibody level (percent binding). Treatment-emergent antidrug antibody can be sub-classified as either treatment-induced (not detected anti-insulin lispro antibody at baseline) or treatment-boosted (detected anti-insulin antibody at baseline):

- treatment-induced response: change from not detected anti-insulin lispro at baseline (Visit 4) to post-baseline detected anti-insulin lispro;
- treatment-boosted response: change from detected anti-insulin lispro at baseline (Visit 4) to post-baseline detected anti-insulin lispro antibody level (percent binding) at least 157% of the baseline value.

The TEADA status during the analysis period will be determined using all data in the corresponding analysis period regardless of IP use. The summary for TEADA status and the anti-insulin lispro antibody level will use the same analysis data.

The number and percentage of patients with positive TEADA response at Visit 4, Visit 13 and Visit 801 will be summarized by treatment group. For patients with positive TEADA response, the number and percentage of patients with positive insulin cross-reactivity will also be summarized by treatment group. Treatment groups will be compared by Fisher’s exact test.

Both actual and change from baseline (Visit 4) for the anti-insulin lispro antibody level in percent binding will be summarized by scheduled visit prespecified in the protocol for patients with positive TEADA response from Visit 4 to Visit 801. The repeated measurement from Visit 4 to Visit 801 will be analyzed by an MMRM model with treatment, baseline value of the response variable, visit, and visit by treatment interaction as fixed factors and patient as the random factor. The ANCOVA model using treatment and baseline value as covariates will be

used for the analysis of last non-missing observation prior to or at Visit 801 and the analysis of maximum percent binding during the analysis period of Visit 4 to Visit 801.

A listing of anti-insulin lispro antibody at each visit will be provided. The listing will include anti-insulin lispro antibody status (detected/not detected), anti-insulin lispro antibody percent binding, TEADA status (positive/negative), insulin cross-reactivity status, and insulin cross-reactivity percent binding for the safety population.

Subgroup analysis for the following selected efficacy and safety variables will be performed by the TEADA status during the analysis period of Visit 4 to Visit 801:

- HbA1c and change from baseline in HbA1c
- 1-hour and 2-hour PPG
- basal, prandial, and total insulin dose
- treatment-emergent infusion site reaction and hypersensitivity reaction
- event rate of all documented hypoglycemic events

The analyses for HbA1c and change from baseline in HbA1c will be performed using an MMRM model for the primary analysis and the HbA1c data prior to permanent discontinuation of IP. The model will include additional fixed terms of subgroup, subgroup by treatment interaction, subgroup by visit interaction, and 3-way interaction of treatment, subgroup and visit.

The PPG will be analyzed by the ANCOVA model same as the model specified in Section 6.11.2 using the efficacy estimand. The model will include additional terms of subgroup, subgroup by treatment interaction, subgroup by visit interaction, and 3-way interaction of treatment, subgroup and visit.

The subgroup analysis for insulin dose will use the MMRM model specified in Section 6.11.4 using the efficacy estimand. The model will include additional fixed terms of subgroup, subgroup by treatment interaction, subgroup by visit interaction, and 3-way interaction of treatment, subgroup and visit.

The treatment-emergent infusion site reaction and hypersensitivity reaction will be analyzed by a logistic regression model including terms of treatment, subgroup, treatment by subgroup interaction. All data regardless of IP use will be used for this analysis.

The negative binomial regression model with treatment with additional terms of subgroup, treatment by subgroup interaction will be used for the subgroup analysis of all documented hypoglycemia event rate while on IP.

The interaction effects (3-way for MMRM and 2-way for ANCOVA/logistic regression model/negative binomial regression model) will be evaluated using a significance level of 0.10, unadjusted. If the interaction effect is significant ($p < 0.10$), separate analysis without the terms related with the subgroup will be performed for each subpopulation.

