14. To compare LY900014 and Humalog with respect to the duration of time spent in hypoglycemic glucose ranges, obtained from CGM use	14. Duration (in minutes) and percentage of time with glucose values <54 and <70 mg/dL (3.0 and 3.9 mmol/L), normalized to a 24-hour period and number of episodes, defined as at least 10 consecutive minutes <54 and <70 mg/dL, from each 14-day CGM session at Week 16
15. To compare LY900014 and Humalog with respect to the duration of time spent in hyperglycemic glucose ranges, obtained from CGM use	15. Duration (in minutes) and percentage of time with glucose values >180 and >250 mg/dL (10.0 and 13.9 mmol/L), normalized to a 24-hour period and number of episodes, defined as at least 10 consecutive minutes >180 and >250 mg/dL, from each 14-day CGM session at Week 16
16. To compare LY900014 and Humalog with respect to the incidence and rate of pump occlusion alarms that lead to an unplanned infusion set change	16. Rate (events/patient/30 days) and incidence (percent of patients with at least 1 event) of pump occlusion alarms that lead to an unplanned infusion set change from baseline through Week 16
17. To compare LY900014 and Humalog with respect to the incidence and rate of episodes of unexplained hyperglycemia that lead to an unplanned infusion set change	17. Rate (events/patient/30 days) and incidence (percent of patients with at least 1 event of unexplained hyperglycemia > 300 mg/dL confirmed by SMBG that leads to an unplanned infusion set change from baseline through Week 16
Tertiary/Exploratory	
18. To compare the safety of LY900014 and Humalog	18. Adverse events, vital signs, chemistry, and hematology laboratory measures
19. To compare the incidence of treatment-emergent positive anti-insulin lispro antibodies for LY900014 and Humalog	19. Incidence of treatment emergent anti-insulin lispro antibodies
20. To compare LY900014 and Humalog with respect to quality of life as measured by the EQ-5D-5L	20. Change from baseline in EQ-5D-5L UK-population-based health state index score and EQ-VAS score at Week 16.
21. To compare LY900014 and Humalog with respect to diabetes treatment satisfaction as measured by the ITSQ	21. Change from baseline in ITSQ regimen inconvenience and lifestyle flexibility domain scores at Week 16

22. To compare LY900014 and Humalog with respect to changes in body weight	22. Change in weight (kg) from baseline to Week 16

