Health outcomes: ITSQ, EQ-5D-5L, EQ-VAS	All Randomized Patients with a baseline and a post-baseline observation	Last of Visits 2-4 prior to initiation of IP	Last of Visits 5-13 prior to discontinuation of IP
Safety Laboratory Tests (chemistry, hematology) – continuous analysis	All Patients in the Safety Population with a baseline and a post-baseline observation	Visit 1	Visit 13 (planned) AND last of Visits 5-13 (planned including early discontinuation visits) regardless of IP use
Safety Laboratory Tests (chemistry, hematology) – categorical analysis	All Patients in the Safety Population with a normal baseline (with respect to the direction being analyzed) and a post-baseline observation	Visits 1-4 (including unplanned tests)	Visits 5-13 (including unplanned tests) regardless of IP use
TEAEs	All Patients in the Safety Population	Prior to first dose of randomized IP (or Visit 4 date if the dose date is missing) but after the first dose of open-label insulin lispro in the Lead-in Period	From first dose of randomized IP to last dose of randomized IP AND From first dose of randomized IP to Visit 801
Hypoglycemia events	Safety Population	All Visits 2-4	All Visits 5-13 prior to discontinuation of IP
Unplanned infusion set changes	Safety Population	All Visits 2-4	All Visits 5-13 prior to discontinuation of IP
Weight and vital signs	All Patients in the Safety Population	Last of Visits 2-4	Visits 5-13 prior to discontinuation of IP

	with a baseline and a post-baseline observation		
Anti-insulin lispro antibodies	Safety Population	Visit 4	Visits 5-801 regardless of IP use

Abbreviations: 1,5-AG = 1,5-Anhydroglucitol; AIT = active insulin time; ANCOVA = analysis of covariance; CR = carbohydrate ratio; EQ-5D-5L = European Quality of Life – 5 Dimensions 5 Level; EQ-VAS = EuroQol visual analogue scale; HbA1c = hemoglobin A1c; IP = investigational product; ISF = insulin sensitivity factor; ITSQ = Insulin Treatment Satisfaction Questionnaire; ITT = intention-to-treat; LOCF – last-observation-carried forward; MMTT = mixed meal tolerance test; MMRM = mixed-effect model repeated measures; PPG = postprandial glucose; SMBG = self-monitored blood glucose; TEAE = treatment-emergent adverse event.

¹ If the percentage of the patients with missing MMTT data at baseline is higher than 15%, a constrained longitudinal data analysis model (Liu et al. 2009; Lu 2010) will be used instead. See Section 6.11.2.

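### Antibody cross-reactivity and, on the natural reading, antibody level are compared between arms only in TEADA-positive patients; these are not randomised comparisons and need an all-patient counterpart

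*SAP*

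**What the plan says.** SAP Section 6.12.7.1 defines a positive treatment-emergent antidrug antibody (TEADA) response in two ways. A patient with no antibody detected at Visit 4 becomes positive on any later detection. A patient with antibody detected at Visit 4 becomes positive on a "post-baseline detected anti-insulin lispro antibody level (percent binding) at least 157% of the baseline value".

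Four analyses follow.

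- **Incidence.** "The number and percentage of patients with positive TEADA response at Visit 4, Visit 13 and Visit 801 will be summarized by treatment group". The arms are compared by Fisher's exact test. This is protocol objective 19 (Protocol Section 4, Table ITRO.2, tertiary/exploratory): "Incidence of treatment emergent anti-insulin lispro antibodies".
- **Cross-reactivity.** "For patients with positive TEADA response, the number and percentage of patients with positive insulin cross-reactivity will also be summarized by treatment group". The Fisher sentence comes after this one and so covers it too.
- **Level.** Actual and change-from-baseline percent binding "will be summarized by scheduled visit prespecified in the protocol for patients with positive TEADA response from Visit 4 to Visit 801". Then: "The repeated measurement from Visit 4 to Visit 801 will be analyzed by an MMRM model with treatment, baseline value of the response variable", with visit and visit-by-treatment terms, plus ANCOVA on the last and on the maximum value. Neither model sentence states a population.
- **Subgroups.** Analyses of HbA1c, 1- and 2-hour PPG, insulin dose, infusion site and hypersensitivity reactions, and documented hypoglycemia "will be performed by the TEADA status during the analysis period of Visit 4 to Visit 801".

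Table ITRO 6.2 (SAP Section 6.1) gives the Safety Population for anti-insulin lispro antibodies, with post-baseline data from "Visits 5-801 regardless of IP use". Antibody level and cross-reactivity for the whole Safety Population otherwise appear only in a listing.

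**The concern.** A treatment comparison within TEADA-positive patients selects on the outcome being compared. Patients enter the analysis because their post-baseline percent binding is newly detectable or has risen by a set ratio. If LY900014 changes antibody level, it also changes who enters the subset, so the two subsets are no longer randomised groups. A null result there may be selection rather than similarity of the formulations, and a difference there cannot be read as a treatment effect. SAP Section 6.1 applies a two-sided 0.05 test by default, so p-values will be attached to these contrasts.

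The subgroup use raises a separate issue. Protocol Section 9.8 forgoes a neutralisation assay and relies on insulin dose and HbA1c to reveal any neutralising effect. The TEADA subgroup analyses are where the SAP links antibody status to those outcomes. Visit 801 falls 4 weeks after Visit 13, when study insulin has stopped and patients are back on their pre-study analog (Protocol Sections 5.3.1 and 7.2.1.5). A patient first positive at Visit 801 is therefore classed as positive for outcomes measured earlier, on IP. That would tend to blur a real association.

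**Working it through.** **Figures in the plan.** The documents give no antibody incidence, level, variance, detection rate or power, so there is no planned figure to reproduce. From them come the 157% rule, the newly-detected rule, 184 completers per arm, 420/2 = 210 randomised per arm, and two-sided alpha of 0.05. All antibody distributions below are assumptions.

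**Closed-form case.** Assume every patient is detected at baseline, the log ratio to baseline is normal with SD 0.6, and LY900014 raises its mean by 0.2. The threshold is c = ln 1.57 = 0.451. With a = (c − μ)/σ, the TEADA rate is 1 − Φ(a), and the mean among positives is μ + σφ(a)/(1 − Φ(a)).

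- Humalog: a = 0.451/0.6 = 0.752; rate 22.6%; mean among positives 0.798.
- LY900014: a = (0.451 − 0.2)/0.6 = 0.418; rate 33.8%; mean among positives 0.849.
- Difference among positives: 0.849 − 0.798 = 0.051, and 0.051/0.2 = 26% of the true shift.
- Power in all patients: SE = 0.6 × √(2/184) = 0.0626; 0.2/0.0626 = 3.20; Φ(3.20 − 1.96) = 89%.
- Power among positives: about 42 and 62 patients, SDs 0.288 and 0.319, SE 0.060, ratio 0.85; power about 13-14%.
- Power of the planned incidence test, 22.6% against 33.8%: about 67% by normal approximation, about 62% for Fisher's exact test.

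Over SD 0.4-0.8 and shift 0.1-0.3, the retained share is 20-29%. This narrow range depends on everyone being detected at baseline, which ignores the newly-detected route to TEADA.

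**Simulation with both TEADA routes.** Settings: 210 per arm, 400 replicates per setting, between-patient SD of log binding 1.0, a detection limit, two post-baseline visits, and ANCOVA on baseline in all patients and in TEADA-positives.

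| Assumed mechanism | Detected at baseline | Share of all-patient difference kept in TEADA-positives |
|---|---|---|
| Uniform log shift 0.15-0.5 | 30% | 79-103% |
| Same | 50% | 57-71% |
| Same | 70% | 49-59% |
| Same | 90-97% | 39-49% |
| 10-25 points more responders, same rise (0.9 log), SD of log change 0.05-0.15 | 90-97% | 4-32% |
| Same, SD 0.05-0.15 | 50% | 21-61% |
| Same, SD 0.3-0.5 | 30-70% | 69-129% |

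Power in TEADA-positives was below all-patient power in every setting. For example, with shift 0.3, 50% detected and SD 0.3, it was 50% against 100%; Fisher's test on incidence also had 100%. Across settings, Fisher's test was mostly within about 15 points of the all-patient ANCOVA, and at worst about 24 points lower.

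**Cross-reactivity.** Assume TEADA in 20% and 35%, with 60% of positives cross-reactive in both arms. The planned table shows 60% against 60%. Per all patients it is 0.20 × 0.60 = 12% against 0.35 × 0.60 = 21%, with power about 70% at 210 per arm.

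**Visit 801.** In the TEADA subgroup analyses, HbA1c uses data before permanent discontinuation of IP, PPG and dose use the efficacy estimand, and hypoglycemia is counted while on IP. Infusion site and hypersensitivity reactions use all data regardless of IP use. Status through Visit 801 matches the data window of the reactions but not that of the other four.

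**The case against.** Four objections carry weight.

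First, a reader might infer that the plan hides most of a true difference in antibody response. The documents do not support that. TEADA incidence is compared by Fisher's test before any conditioning and is the protocol's immunogenicity endpoint. In the closed-form case it would show 23% against 34%. Nor is a large loss in the level contrast general: it needs nearly all patients detected at baseline, or arms that differ mainly in how many respond, with little noise. Both answers stand. The incidence test does not, however, say how high levels go or how many of all patients become cross-reactive.

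Second, the restriction to TEADA-positives grammatically governs the descriptive sentence only, and Table ITRO 6.2 lists the Safety Population. If the models use that population, the criticism of them reduces to unclear wording. The subset is the natural reading because the model sentences name nothing else, but it is not certain. The cross-reactivity restriction is explicit.

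Third, Protocol Section 9.8 characterises cross-reactivity only in positive samples, so some conditioning comes from the assay. That limits the numerator; it does not prevent an all-patient denominator.

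Fourth, assessment up to Visit 801 is prespecified and suits the reactions analysed regardless of IP use. That stands for those reactions and for incidence, but not for the on-IP outcomes.

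**Conclusion.** The point holds as a minor one. The cross-reactivity comparison, and on the natural reading the antibody-level models, condition on a post-randomisation status built from the same percent-binding values. They are not randomised comparisons, they lose power, and they may understate or distort a difference in level. The retained share of about 4% to 129% rests wholly on assumed detection rates, noise and mechanisms, so no single figure should be quoted for this trial. The incidence comparison is unaffected.

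The Visit 801 mismatch in the subgroup analyses is a separate defect. It follows from the text alone, and its size cannot be estimated from the documents. Priority is low because the endpoint is exploratory and outside the multiplicity scheme.

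**What to change.** Amend SAP Section 6.12.7.1 and reconcile it with Table ITRO 6.2:

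- State the population for the MMRM and ANCOVA. Make the treatment comparison of percent binding in all Safety-population patients with a baseline and a post-baseline sample, with a prespecified rule for not-detected values and a sensitivity check on that rule.
- Report cross-reactive TEADA with all evaluable Safety-population patients as denominator.
- Keep the TEADA-positive-only tables of level and cross-reactivity as description, without p-values.
- For subgroup analyses of on-IP outcomes (HbA1c, PPG, dose, hypoglycemia), use TEADA status through Visit 13, with the Visit 801-inclusive version as supportive. Retain the latter for reactions analysed regardless of IP use.
- While editing, drop Visit 4 from the TEADA counts: TEADA is a change from Visit 4 and is undefined there.

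The cost is SAP wording, with no new data. The downside is that many low or not-detected values enter the level model. The assay is semiquantitative and the documents give no lowest reportable value, so the rule for not-detected results has to be settled with the laboratory.
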